5.1 Imaging assessments

The following study assessments will be obtained. The timings of these assessments are detailed in the Study Plan (Table 1).

- MRI assessment

Patients will undergo a pre-scan check prior to an MRI scan of the brain. Patients will be asked to lie on their back in the MRI scanner where a head coil will be placed over the head and shoulders. During the scan, the patients will undergo an IV injection of gadolinium contrast agent. The scans will be used for BM assessments by CNS RECISTv1.1 (Eisenhauer et al 2009) delineation of brain lesions regions for corresponding PET analysis and to examine BBB breakdown.

- Thorax/Abdomen CT

Patients will undergo a thorax/abdomen CT scan, including chest and abdomen and pelvis if there is disease present. The scans will be used for extra-cranial tumour assessments according to RECSIT v1.1. Additional CT scans, including neck region, may be included depending on metastasis location.

- PET examinations

Brain PET examination procedures will include IV administration of [^{11}C]osimertinib followed by brain radioactivity measurements using the HRRT PET system and radioactivity measurements in blood (arterial and venous) (for detailed description see Section 5.3.2.2).

5.2 Safety assessments

5.2.1 Laboratory safety assessments

Blood and urine samples for determination of clinical chemistry, haematology, and urine analysis will be taken during Visit 1 as indicated in the Study Plan.

The date and time of each collection will be recorded in the appropriate pCRF.

Following a review of data from a group of patients, the timing of blood samples may be adjusted for subsequent groups of patient.

The following laboratory variables will be measured:

Table 2 Laboratory safety variables

Clinical chemistry (2.7 mL sample)	Haematology (2.7 mL sample)
S/P-Albumin	B-Hb
S/P-ALT	B-Leukocyte
S/P-AST	B-Absolute leukocyte differential count: neutrophils, lymphocytes, monocytes, basophils, eosinophils
S/P-Alkaline phosphatase	B-Platelet count
S/P-Bilirubin, total	B-Red cell count
S/P-Calcium, total	B-Hematocrit (PCV)
S/P-Creatinine	Coagulation (1.8 mL sample)
S/P-Glucose	PT/INR
S/P-Magnesium	aPTT/TT
S/P-Phosphate	Urine analysis (dipstick):
S/P-Potassium	U-Hb/Erythrocytes/Blood
S/P-Sodium	U-Protein/Albumin
Serology screen (1.8 mL sample)	U-Glucose
HBC, HCV, HIV	U-Leucocytes
	U-Nitrites
Pregnancy test	
Blood or urine	

aPTT: Activated partial thromboplastin time; ALT: Alanine aminotransferase; AST: Alkaline phosphatase; B: Blood; Hb: Haemoglobin; HBC: Hepatitis B virus; HCV: Hepatitis C virus; HIV: Human immunodeficiency virus; INR: International normalised time; P: Plasma; PCV: Packed cell volume; PT: Prothrombin time; S: Serum; TT: Thrombin time; U: Urine.

Please Note. In case a patient shows an AST **or** ALT $\geq 3 \times \text{ULN}$ **or** total bilirubin $\geq 2 \times \text{ULN}$ please see Appendix D ‘Actions required in cases of combined increase of aminotransferase and total bilirubin – Hy’s Law (HL), for further instructions.

5.2.2 Physical examination

A complete physical examination will be performed during Visit 1 as indicated in the Study Plan (Table 1) and include an assessment of the following: general appearance, skin, head and neck (including ears, eyes, nose and throat), respiratory, cardiovascular, abdomen, lymph nodes, thyroid, musculoskeletal (including spine and extremities) and neurological systems. The anaesthesiologist will perform the Allen’s test to make sure there is normal flow in the wrist between radial and ulnar arteries.

Any new or aggravated clinically relevant abnormal medical finding at a physical examination as compared with the baseline assessment will be reported as an AE.

5.2.3 ECG

Twelve-lead ECGs will be obtained after the patient has been resting semi-supine for at least 10 minutes. All ECGs should be recorded with the patient in the same physical position. For each time point 3 ECG recordings should be taken at about 5 minute intervals. A standardised ECG machine should be used and the patient should be examined using the same machine throughout the study if possible.

After paper ECGs have been recorded, the Investigator or designated physician will review each of the ECGs and may refer to a local cardiologist if appropriate. A paper copy should be filed in the patient’s medical records. If an abnormal ECG finding at screening or baseline is considered to be clinically significant by the Investigator, it should be reported as a concurrent condition. For all ECGs details of rhythm, ECG intervals and an overall evaluation will be recorded.

ECG data will be collected digitally and will be transferred electronically for central analysis as described in the study specific ECG manual. The investigator may choose to perform a non-digital ECG at the time of the screening visit in order to identify patients eligible for study entry. If a non-digital ECG is performed at the screening visit it cannot subsequently be used as a baseline recording, in this situation an ECG will need to be collected on the baseline visit in digital form.

Heart rate, PR, R-R, QRS and QT intervals will be determined and reviewed by an external cardiologist.

If there is a clinically significant abnormal ECG finding during the treatment period, this should be recorded on the AE pCRF, according to standard AE collection and reporting processes (see Section 6.3.6). A 28-day follow-up assessment will be required if an on-treatment assessment was abnormal at the time of discontinuation of the IP or study, to confirm reversibility of the abnormality. Information on osimertinib dose reduction for QTc interval prolongation is detailed in Section 6.8.4.

5.2.4 Echocardiogram/ MUGA scan

An ECHO or MUGA scan to assess LVEF will be performed at screening (prior to first dose of TAGRISSO) and at least every 16 weeks throughout the treatment period. The modality of the cardiac function assessments must be consistent within a patient ie, if echocardiogram is used for the screening assessment then ECHO should also be used for subsequent scans. The patients should also be examined using the same machine and operator whenever possible, and quantitative measurements should be taken. A 28-day follow-up assessment will be required if an on treatment assessment was abnormal at the time of discontinuation of study therapy, to confirm reversibility of the abnormality

5.2.5 Vital signs

Vital signs will be measured at the times specified in the Study Plan (Table 1) and recorded in the pCRF. However, the Investigator reserves the right to add extra assessments if there are any abnormal findings for any reason the Investigator feels meets this requirement.

5.2.5.1 Pulse and blood pressure

Supine BP and pulse/heart rate will be measured using a semi-automatic BP recording device with an appropriate cuff size after the patient has rested for approximately 10 minutes.

As a guide, any readings outside the following should be considered in the evaluation:

- Systolic BP >140 mmHg
- Diastolic BP >90 mmHg
- Heart rate <35 bpm or >100 bpm

5.2.5.2 Body temperature

Body temperature will be measured using a semi-automatic body temperature recording device in accordance with local practice.

5.2.5.3 Height and weight

Height (cm) and weight (kg) will be evaluated at screening and BMI (kg/m^2) will be calculated. Patients will be required to remove their shoes and wear light indoor clothing for these measurements.

5.3 Other assessments

5.3.1 Ophthalmologic exam

Full ophthalmic assessment, including slit lamp examination, should be performed at screening and if a patient experiences any visual symptoms (including blurring of vision), with additional tests if clinically indicated. Ophthalmology examination results should be collected in the pCRF.

Any clinically significant findings, including those confirmed by the ophthalmologist must be reported as an AE. Photographs should be performed to record any clinically significant

findings. These photographs should be available for central review by AstraZeneca and AstraZeneca representatives if necessary.

Patients experiencing corneal ulceration will not be permitted to restart study treatment.

5.3.2 Imaging assessments

5.3.2.1 MRI assessment

As part of the inclusion process, all patients will undergo an MRI scan to exclude macroscopic pathology (stroke, diffuse white matter, vascular changes) and confirm the presence of BM. Magnetic resonance images will also be used as anatomical reference for PET examinations.

The examinations will be done at the MRI centre, PPD ██████████ using the 3.0T system using the clinical routine MRI protocol as defined at PPD ██████████ ██████████. This includes a high resolution T1 sequence, T2 sequences and a gadolinium enhanced T1 sequence and DWI (but not limited to these).

5.3.2.2 PET examination procedures

The PET examinations will be performed at the PET centre, Karolinska Institutet, Department of Clinical Neuroscience, PPD ██████████, Solna, Sweden.

PET examinations will include radioactivity measurements in blood and in the brain. Prior to brain PET examinations, a plastic helmet will be made for each patient individually for use during the PET examinations in order to minimize head movement. Brain PET examinations will be performed using a HRRT PET system (Siemens Molecular Imaging, Knoxville, TN, US). The patient will be placed recumbent with his/her head in the PET system. After the IV injection of [¹¹C]osimertinib emission data will be acquired in list mode over 90 minutes.

During the PET examination time, a series of arterial blood samplings will be taken to measure radioactivity and radiometabolites of [¹¹C]osimertinib. The purpose of blood measurements is to obtain a metabolite-corrected arterial input function which is used for the kinetic compartment analysis of [¹¹C]osimertinib brain exposure. The anaesthesiologist will perform the Allen's test to make sure there is normal flow in the wrist between radial and ulnar arteries. An arterial cannula will be inserted in the radial or brachial artery of 1 of the arms (the non-dominant arm if possible) under local anaesthesia. A venous cannula will be inserted in another arm for the administration of [¹¹C]osimertinib .

An arterial cannula will be used for arterial blood sampling during the PET examination time (first 10 minutes automatic blood sampling system [ABSS], followed by manual blood samples according to predefined KI PET centre protocol; at approximately 2, 4, 6, 8, 10, 15, 20, 25, 30, 40, 50, 60, 75 and 90 minutes post-[¹¹C]osimertinib injection). A venous cannula will be used for the bolus injection of [¹¹C]osimertinib, after it is dissolved in a sterile physiological phosphate buffer (pH 7.4). The mass of the tracer injected per single measurement will be less than 10 µg, the radioactivity per single injection will not exceed 330 MBq/70 kg of body weight. The cannula will be immediately flushed with 10 mL saline.

The collection of arterial and venous samples is required at PET1 and PET2 examinations for analysis. However, based on the preliminary data analysis in the first microdosing study in healthy patients, arterial assessments may be removed for PET3 examination.

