j Required at baseline. Repeated during the imaging phase only if clinically indicated at any time point or subsequently at follow-up 30 (± 7) days after last administration of study medication (for example to follow up on a cardiac AE).

k Patient must weigh at least 40.0 kg and no more than 100.0 kg (see Section 3.1).

l Blood and urine samples will be collected for routine laboratory testing (haematology, clinical chemistry), and urine analysis (see Section 5.4).

m Serum pregnancy test at screening and follow-up. FSH and LH to be tested at screening. All other visits, urine pregnancy test.

n Current medications will be reviewed and recorded.

o PK sampling: at pre-administration, 2, 4 and 7.5 hour(s) (can be modified if necessary). During PET examinations, PK sampling schedule maybe limited to the PET examination time (see Section 5.3.2.2).

p CSF samples will be collected at pre-administration prior to start of treatment and at the PET3 examination day.

q A re-biopsy from tissue may be collected as part of clinical routine upon disease progression during continued access treatment. A blood sample (2 x 10 mL) will be collected at screening only for additional option for central confirmation of EGFR status if tissue confirmation is not possible.

r An arterial line will be inserted on the day the patient arrives for the administration of the IP and PET examination. The arterial line will be placed in the opposite arm than the 1 being used to administer the single IV microdose of [¹¹C]osimertinib bolus injection. A venous access line will also be inserted to collect blood samples. The arterial line will be removed at the conclusion of the PET examinations, after the last sample has been collected. The placement of the arterial line, venous access line, administration of the IV microdose [¹¹C]osimertinib bolus injection, PET examinations (see Section 5.3.2.2), and removal of the arterial line (and venous access line) will take place on the same day. Standard institutional procedures will be followed for arterial line removal. In case of failure with arterial sampling during the PET examination, because of spasm or blood clots, the PET examination will continue and venous samples will be taken according to the planned schedule of arterial samples.

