s Arterial blood sampling for [¹¹C]osimertinib will occur at approximately 2, 4, 6, 8, 10, 15, 20, 30, 40, 50, 60, 75, and 90 minutes post-[¹¹C]osimertinib injection. Venous blood samples will be collected at 30, 60 and 90 minutes. In case of failure to sample arterial blood (eg, spasm, occlusion) the arterial blood sampling may be substituted by venous blood samples throughout the PET examination. The blood sampling schedule may be adjusted at the Investigator's discretion, but will not exceed 120 mL per patient per measurement (see point i, in case of failure of arterial sampling).

t If a patient cannot undergo the PET examination at the scheduled time or if technical failure occurs, eg, camera breakdown or radioligand synthesis failure, the patient will be discharged and the visit rescheduled to a later time point. PET examinations will continue over 90 minutes (minimum 60 minutes). If examination duration becomes shorter due to the technical or patient-related reasons, the data will be inspected and if quantitative analysis will not be possible, the measurement maybe rescheduled. In case of radiosynthesis failure and if radioactivity available for injection will be below 200 MBq (per 70 kg body weight), the PET examination will be rescheduled and the patient will be invited to participate on an additional visit. In case of technical failure on examination days, please contact AstraZeneca for alternate examination days.

u Osimertinib 80 mg once a day will be taken by the patient from the day of the second PET examination for at least 21 days before the PET3 examination will be scheduled. On Day 14 (± 2 days), a clinical visit to evaluate the safety of the patient will be performed.

v AEs will be assessed. SAEs will be collected from the time of signature of informed consent throughout the treatment period and including the follow up period. AEs will be collected throughout the study, from informed consent until the end of the follow up period. The follow-up period is defined as 30 working days after the IP is discontinued.

w A post study assessment will be performed within 30 working days after the IP has been infused and last PET examination completed. In the event of a holiday or weather delay, the follow-up visit may be postponed 1 to 2 working days (see Section 4.4).

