5.8 Volume of blood

The number of blood samples that will be drawn from each patient is shown in Table 3. Additional details will be described in a separate Laboratory Manual.

Table 3 Volume of blood to be drawn from each patient

Assessment	Sample volume (mL)	No of samples	Total volume (mL)
Blood chemistry	2.7	5	13.5
Coagulation	1.8	3	5.2
Haematology	2.7	5	13.5
Serology	1.8	1	1.8
Osimertinib PK	2	10 (5×2)	20
Biomarkers	20	5	100
EGFR mutation	20	2	40
Arterial blood radioactivity measurements	25	2 (or 3)	75 (or 100)
Arterial blood radioactivity and metabolite measurements (manual blood samples)	2	20 (or 30)	40 (or 60)
Arterial blood radioactivity and metabolite measurements (manual blood samples)	4	8 (or 12)	32 (or 48)
Venous blood radioactivity and metabolite measurements	4	18 (or 24)	72 (or 108)
Total	86	79 (100)	413 (or 510)

ABSS: Automatic blood sampling system; PET: Positron emission tomography; PK: Pharmacokinetics.

Note: arterial blood sampling includes ABSS used for the first 5 minutes, 5 mL/min. Manual blood samples will be in the range of 2 to 4 mL, not exceeding 40 mL. The study will include 2 PET examinations with arterial blood sampling and the third PET examination may omit arterial blood sampling.

Additional 50 mL blood may be drawn if repeated laboratory tests are needed or if PET examination protocol needs adjustment. The maximum volume to be drawn from each patient will not exceed 550 mL.

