8.5.7 Quantitative PET brain imaging data analysis

PET image data analysis includes sequential steps:

[figure not shown]
- (i) Image pre-processing (re-orientation, re-alignment, co-registration to MR images, etc.)
- (ii) Manual or/and automatic delineation of the anatomical and tumour ROIs
- (iii) Extraction of regional radioactivity (time activity curves)
- (iv) Preparation of arterial input function using conventional PET analysis methods and
- (v) Quantification of [^{11}C]osimertinib distribution in the brain

A set of exposure parameters including but not limited to will be quantified:

- C_{\max} , %ID brain (%ID)
- C_{\max} , SUV brain (SUV)
- T_{\max} brain (min)
- Brain plasma partition coefficient (concentration brain/plasma ratio) as ($AUC_{\text{brain } 0-90\text{min}}/AUC_{\text{blood } 0-90\text{min}}$)

For detailed description of quantitative analysis methods see Section 5.3.2 and Saleem A, Searle GE, Kenny LM, Huiban M, Coombes RC, et al. Lapatinib access into normal brain and brain metastases in patients with Her-2 overexpressing breast cancer. EJNMMI Res. 2015; April 30;5:20.

Schou et al 2015.

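### If arterial sampling is dropped at PET3, does the plan need a written rule for deriving the PET3 Kp and V_T?

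*Protocol*

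**What the plan says.** The option to drop arterial sampling appears twice. Protocol 5.3.2.2 requires arterial and venous samples at PET1 and PET2 and then says: "However, based on the preliminary data analysis in the first microdosing study in healthy patients, arterial assessments may be removed for PET3 examination". The note under Protocol Table 3 (section 5.8) repeats that "the third PET examination may omit arterial blood sampling".

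The analysis is written around arterial data. Protocol 5.3.2.2: "The purpose of blood measurements is to obtain a metabolite-corrected arterial input function". Step (iv) of Protocol 8.5.7 is "Preparation of arterial input function using conventional PET analysis methods", with no alternative listed. SAP 3.1 defines Kp as brain AUC divided by plasma AUC, both over 0 to 90 minutes by the linear trapezoidal rule, and V_T as a compartment-model quantity. It makes no exception for PET3.

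For venous tracer blood, footnote s to Protocol Table 1 says: "Venous blood samples will be collected at 30, 60 and 90 minutes". Footnote r covers arterial failure during a scan, when "venous samples will be taken according to the planned schedule of arterial samples".

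There is also room to adapt. Footnote s: "The blood sampling schedule may be adjusted at the" discretion of the investigator. The Table 3 note: "Additional 50 mL blood may be drawn if repeated laboratory tests are needed or if PET examination protocol needs adjustment". A note in SAP 3.1 foresees that PET variables may change with the emerging data and the kinetic approach chosen, through a SAP amendment.

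**The concern.** Kp is a primary outcome measure, and hypothesis 2 in Protocol 1.2 sets exposure at steady state (PET3) against exposure after one dose (PET2). If PET3 has no arterial curve, V_T has no named input, and the plasma AUC under Kp has no named source.

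The routine venous samples start at 30 minutes, so they miss the period just after the bolus. An analyst who ran a 0-90 trapezoid through those three points would usually get too small a denominator. PET3 Kp would then rise for a reason unrelated to the drug, in the direction that hypothesis 2 favours. With a target of 8 evaluable patients, a table mixing the two bases could mislead.

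The venous row of Table 3 adds doubt, because it can be read as budgeting no venous tracer samples at PET3.

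**Working it through.** **1. What is scheduled.** Protocol Table 1 marks arterial catheter and sampling, venous tracer sampling, tracer injection and PET at PET1, PET2 and PET3. The default is therefore full sampling at PET3. The sentence in 5.3.2.2 that permits removal names arterial assessments only.

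**2. Which outcomes need blood.** Maximum %ID, maximum SUV and time of maximum come from the image, injected radioactivity and body weight. Kp and V_T need blood. V_T is in SAP 3.1 but is not among the measures listed in Protocol 2.1 or 8.4, although the 8.4 list is open-ended.

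**3. Is there room for a fuller venous curve?** From Table 3, the manual arterial samples for one scan are the difference between the three-scan and two-scan figures:

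- count: (30 - 20) + (12 - 8) = 14, which matches the 14 manual times in 5.3.2.2;
- volume: (60 - 40) + (48 - 32) = 36 mL.

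Drawing those 14 samples from a vein at PET3 would take 36 mL. That is inside the extra 50 mL in the Table 3 note and the 120 mL per-measurement limit in footnote s. Added to the printed lower total, 413 + 36 = 449 mL, below the 550 mL ceiling. A full venous curve is feasible. Whether it would agree with an arterial one is not known from the documents.

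**4. Can Table 3 show that venous samples stop at PET3?** The printed rows add up to the printed totals: 413 (or 510) mL and 79 (or 100) samples. Three rows do not equal volume times number:

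| Row | Volume x number | Printed |
|---|---|---|
| Coagulation | 1.8 x 3 = 5.4 | 5.2 |
| Arterial, 25 mL | 25 x 2 = 50; 25 x 3 = 75 | 75; 100 |
| Venous, 4 mL | 4 x 18 = 72; 4 x 24 = 96 | 72; 108 |

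Using products throughout, the totals would be 388.2 and 473.2 mL. The venous volume rises by 108/72 = 1.5, like the manual arterial rows, which suggests samples at two scans or three. But the venous count rises by 24/18 = 1.33, as does the 25 mL arterial volume (100/75 = 1.33). Eighteen is 9 x 2 and also 6 x 3. Footnote s gives three venous times per scan, so 6 or 9 in all, which fits neither figure. The table cannot settle the question; Table 1 does, by scheduling venous samples at PET3.

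**5. How large could the error be?** The documents give no plasma kinetics, so every curve here is an assumption. The trapezoid through 30, 60 and 90 minutes is

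- with C(0) = 0: 30 C30 + 30 C60 + 15 C90;
- with the 30-minute value carried back: 45 C30 + 30 C60 + 15 C90.

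Take one assumed curve: a linear rise to 0.5 min, then three exponentials with amplitudes 6, 1.5 and 1 and half-lives 0.7, 6 and 120 min, venous equal to arterial. Then C30 = 0.893, C60 = 0.711, C90 = 0.596 and the true AUC is 91.05.

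- C(0) = 0: 26.79 + 21.32 + 8.95 = 57.06, so Kp is inflated by 91.05/57.06 = 1.60.
- Carried back: 40.19 + 21.32 + 8.95 = 70.46, so 91.05/70.46 = 1.29.

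Three steeper assumed curves take these factors up to 3.59 and 2.85. Adding an accumulating radiometabolite term brings the lowest carried-back factor to 0.96, which reverses the direction. A separate family of assumed curves with an early peak gives 1.25 to 6.7 with C(0) = 0 and 1.04 to 5.1 carried back. The answer depends almost wholly on the curve assumed, and no section calls for this calculation.

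**The case for a change.** The strongest case for a change is that the omission is foreseen and the analysis has no branch for it. Venous sampling on the arterial schedule is offered only when arterial sampling fails. The schedule adjustment and the extra blood are permissions, not requirements. The SAP note points to an amendment, while the SAP's amendment history is empty and its section 6 reports no changes from the protocol. A rule chosen after PET3 data are seen is weaker than one chosen before.

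The factual part stands: these two documents name no replacement input. They also refer elsewhere for method detail, to cited PET studies (Protocol 8.5.7) and to the PET centre's own sampling protocol (5.3.2.2), which are not available here. So the most that can be said is that the protocol and SAP are silent.

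The candidate additions gain little:

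- Declaring Kp and V_T not derived without arterial data largely repeats SAP 4.2.3. Where it goes further, it keeps out of the summaries venous values that footnotes r and s provide for, at a cost in so small a study.
- A same-basis rule for PET2-PET3 pairs would govern a contrast that the SAP does not define.
- A supportive Kp over 30-90 minutes is a different quantity, 1.4 to 3.4 times Kp 0-90 under the assumed curves.
- A rule for scans of 60 to 89 minutes is a separate matter.

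**Conclusion.** No change to the plan follows. What remains is an unwritten rule for an optional branch of a descriptive study. If arterial sampling is kept at PET3, as Table 1 schedules, the issue does not arise. If it is dropped, the PET centre that derives these parameters has to choose a blood source or leave the values missing. SAP 3.1 already names an amendment as the place for the kinetic modelling choice. A sensible analyst would record that choice there before analysing PET3, label any venous-based value, and avoid reading it against an arterial PET2 value.

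The reach is limited to Kp and V_T at one of three scans. Hypothesis 2, which speaks of exposure in general, can still be described through %ID and SUV. No numerical size can be attached, because the fold-changes rest on assumed curves and an unprescribed calculation. The venous row of Table 3 is a clerical slip that affects no analysis.

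This conclusion assumes that Table 1 governs venous sampling at PET3 and that nobody would run a 0-90 trapezoid through three late venous samples and pool the result with arterial values.
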